In case of worsening, including signs of the secondary bacterial infection, the Investigator may decide on early discontinuation of the study drug. In this case, an unscheduled visit to the trial site is required.

Visit 2 (Day 4):

Visit 2 is conducted on Day 4; the patient must visit the trial site in the fasted state and bring the filled-in diary and unused drug.

If Group B patients (ANTI-ANGIN® FORMULA) did not meet recovery criteria (total $TSS \le 2$) at Visit 2 (Day 4), they will require continuation of the therapy, and some procedures for those patients will be transferred for the next day (Visit 3, Day 5), see below. The patients will keep their diaries and the unused drugs.

Visit 2 procedures for both groups:

- Collection of complaints, actualization of anamnesis;
- Records on the concomitant therapy;
- Physical examination (including oropharynx);
- Measurement of the main vital signs;
- Evaluation of adverse events (including based on results of the throat and pharynx examination);
- Evaluation of exclusion criteria;

 Compliance evaluation (diary completion, administration of the study drugs);

Visit 2 procedures for patients from Group A (Angal S) and Group B (ANTI-ANGIN® FORMULA) who achieved recovery criteria (total $TSS \le 2$):

- Hematology;
- Biochemistry;
- 12-lead ECG;
- Global evaluation of treatment tolerability during the trial by the physician and the patient;
- Return of the unused study drug;
- Return of the patient's diary;

Visit 3 (Day 5):

Evaluation of the disease outcome based on TSS questionnaire for the Group B patients who continued therapy after Visit 2.

- Collection of complaints, actualization of anamnesis;
- Records on the concomitant therapy;
- Physical examination (including oropharynx);
- Measurement of the main vital signs;
- Evaluation of adverse events (including based on results of the throat and pharynx examination);
- Evaluation of exclusion criteria;
- Return of the unused study drug;
- Return of the patient's diary;
- Compliance evaluation (diary completion, administration of the study drugs);
- Hematology;
- Biochemistry;
- 12-lead ECG;
- Global evaluation of treatment tolerability during the trial by the physician and the patient.

Group B patients should complete the therapy on Day 5 (unless it had happened earlier). In case of worsening or preservation of the disease signs by the last therapy day, further treatment will be given in accordance with

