- 6. Use of the systemic, inhalation, or nasal glucocorticosteroids during 30 days before the trial start and/or planned use of the glucocorticosteroids (except for the topical skin drugs) during the trial.
- 7. Impossibility to discontinue other drugs which might influence the trial results, e.g., antiviral or prohibited concomitant drugs (see *Prohibited concomitant therapy* section), for the trial period.
- 8. Signs of a primary bacterial pharyngitis or secondary bacterial infection (including body temperature increase above 37.5 °C, purulent pharyngeal pellicles, significant intoxication, leukocytosis, neutrocytosis, WBC differential's shift to the left (increase in stab neutrophils, presence of younger neutrophils), ESR more than 30 mm/h).
- 9. Granular pharyngitis.
- 10. Signs of rhinitis, sinusitis, otitis, eustachitis, laryngitis, tracheitis, bronchitis (such conditions require therapy which might influence the trial results).
- 11. Phenylketonuria.
- 12. Deficit of saccharase or isomaltase (according to anamnesis data).
- 13. Glucose-galactose malabsorption (according to anamnesis data).
- 14. Fructose intolerance.
- 15. Diabetes mellitus.

	16. Glucose-6-phosphate dehydrogenase deficiency (according to anamnesis data).	
	17. Hemochromatosis.	
	18. Anemia (Hb less than 120 g/l according to hematology test).	
	19. Hyperoxaluria.	
	20. Urolithiasis.	
	21. Myasthenia.	
	22. Severe, uncontrolled, cardiovascular condition which, in the	
	Investigator's opinion, preclude the patient from participation in the trial, namely:	
	 Severe (IV acc. to Canadian Cardiovascular Society) or unstable angina; 	
	b. Decompensated chronic heart failure (NYHA stage IV);	
	c. Myocardial infarction for the last 6 months;	
	d. Uncontrolled arterial hypertension (BP more than 180/115 mm Hg).	
	23. Pregnant and/or breastfeeding women.	
	24. Participation in other clinical trials at the screening visit or for 30 days before the screening visit.	
	25. Surgical intervention for 30 days before the screening visit or planned surgical treatment during the trial (before a follow-up visit is completed), including diagnostic procedures or hospital stay.	
	26. Known or suspected narcotic/alcohol abuse.	
	27. A suspected low compliance or incapability of the patient to perform the procedures and comply with restrictions according to the trial protocol (e.g., due to mental disorders).	

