4.5 Expected duration of the subjects' participation in the trial

Screening period: 1 day.

Treatment period: up to 5 days (including the screening/randomization day).

Follow-up period: up to 2 days.

A maximum duration of each subject's participation: 7 days.

A minimum duration of each subject's participation: 6 days (depending on the arm).

4.6 Description of rules for termination of the trial parts or the trial as a whole

The trial may be terminated on the following grounds:

- 1. Upon the Sponsor's initiative: availability of new toxicological or pharmacological data, or data on SAE which require re-consideration of the previous evaluation of the benefit/risk ratio.
- 2. Upon the Sponsor's initiative: AEs incidence or severity require the trial termination;
- 3. Upon the Sponsor's initiative: other reasons including administrative ones.
- 4. Upon the decision of the regulatory authorities.

The trial may be terminated at a specific trial site in case the patients enrollment or data quality are unsatisfactory, or it is reasonable to assume a breach of GCP and/or Declaration of Helsinki, or other serious protocol deviations.

In case of early termination of the trial, the Sponsor must inform the trial site personnel as well as regulatory authorities with indication of the reason thereof.

The rules for trial termination for every participant are described in Section 5.3.

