5.3 Exclusion criteria

5.3.1 Terms and conditions for the subjects' exclusion from the trial

The subjects may be excluded from the trial on their own free will at any moment, without giving any reason, as well as upon decision of the Investigator or Sponsor in cases when continuation of the participation may inflict harm to the patient's health and/or life. In addition, the patient must be excluded in the cases listed below:

- 1. Negative course of the disease with signs of the secondary bacterial infection (including body temperature increase above 37.5 °C).
- 2. The Ethics Committee, regulatory authorities, or Sponsor terminate the trial or participation of the specific trial site for any reason.
- 3. The Investigator's decision to withdraw the patient from the trial in the interests of the patient.
- 4. Withdrawal of the informed consent (unwillingness of the patient to continue his/her participation in the trial).
- 5. Serious deviation from the trial protocol.
- 6. Individual intolerance of the study drugs.
- 7. Clinically significant adverse event or serious adverse event.
- 8. Patient's non-compliance.
- 9. False inclusion (e.g., the patient was included in breach of the inclusion/non-inclusion criteria).
- 10. The patient complies with the non-inclusion criteria during the trial.
- 11. The patient receives or requires an additional therapy which might influence the trial results or patient's safety (see *Prohibited concomitant therapy* section).

12. Other conditions or events which, in the Investigator's opinion, require the patient's exclusion from the trial.

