6.2.2 Prohibited prior and concomitant therapy

The drugs listed below are prohibited for use throughout the trial period:

- 1. Topical drugs (aerosols, sprays, inhalations, gargle solutions, fast-disintegrating tablets/lozenges/pastilles) in the pharynx or nose.
- 2. Systemic, inhalation, or nasal glucocorticosteroids.
- 3. Systemic or topical (intranasal or pharyngeal) antibacterial drugs.
- 4. Anti-viral drugs.
- 5. Immunomodulatory agents.
- 6. Painkillers or antipyretic agents.
- 7. Class I antiarrhythmics.
- 8. Cholinesterase inhibitors (including neostigmine, distigmine, pyridostigmine) and other drugs for myasthenia.

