9.7 Selection of subjects for analysis

The following data sets will be used for analysis:

• The intention-to-treat (ITT) population: all randomized subjects who received at least one dose of the study drug/placebo and have completed at least one visit aimed at evaluation of the efficacy parameters (i.e., at least all the procedures of Visit 1).

According to the ICH E9 requirements, the ITT population will be considered to be a population for statistical analysis in the equivalence trials (including non-inferiority trials).

- The per protocol (PP) population: all randomized subjects who completed participation in the trial in accordance with the protocol (have completed the prescribed period of treatment and follow-up without significant deviations from the protocol).
- The safety population (safety): All randomized subjects who received at least one dose of the trial/reference drug and have completed at least one visit to the evaluation of the parameters of safety (i.e., at least all the procedures of Visit 1). As distinct from ITT population, the safety population will be analyzed depending on actually received treatment (not only prescribed) (in case of difference between the prescribed and received therapies).

Protocol No. TE_004_ANG_LOZ

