3.2 Serious protocol deviations

A serious protocol deviation (Item 11.3 of the trial protocol) is a deviation, which may, according to the estimate by the Investigator or a person assigned by the Investigator, result into withdrawal of the subject from the trial or withdrawal of his data from the statistical part of the trial. The deviations not referred to as serious ones shall be considered minor protocol deviations.

For the purposes of this analysis, the serious protocol deviations were defined as follows:

Description	Example/Explanation	Efficacy or safety	Excluded from population:
lincilision and non-	Inclusion criterion No. 5: e.g., inclusion of the patient with initial total TSS < 5	Efficiency	PP
Violation of the informed consent receipt procedure	Absence of the Informed Consent Form	Safety and efficacy	All

	Informed Consent Form was signed after randomization/initiation of therapy	Safety and efficacy	None
	Prescription of the drug non-consistent with the randomization arm	Efficiency	PP
	Low compliance: the patient missed more than 3 doses of the study drug	Efficiency	PP
Concomitant drugs	The patient used prohibited drugs during the trial (or had used the drugs prohibited by the inclusion/exclusion criteria before the trial initiation)	Efficacy and safety	PP

A final list of serious protocol deviations will be compiled before the statistical analysis start. Every protocol deviation should be evaluated for the patient's exclusion from the PP data set or statistical analysis by the trial Sponsor representative. The decisions adopted and lists of patients included into the relevant data sets must be documented before the analysis initiation.

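### The per-protocol exclusion for prohibited drugs has no cut-off at the Day 4 score, so treatment started afterwards in patients still ill can decide who is in the PP set

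*SAP*

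**What the plan says.** - **PP exclusion.** The table in SAP 3.2 removes a patient from PP if "The patient used prohibited drugs during the trial", or used them before the trial contrary to the entry criteria. It gives no end date. The same section has a sponsor representative evaluate every deviation for exclusion, with decisions documented before analysis.
- **Length of the prohibition.** Protocol 6.2.2: "The drugs listed below are prohibited for use throughout the trial period". The list includes throat and nasal topicals, antibacterials, antivirals and "Painkillers or antipyretic agents".
- **Length of the trial for a patient.** Protocol 4.5 counts "Follow-up period: up to 2 days" as part of participation, and the synopsis makes follow-up trial period III. The surgery criterion among the non-inclusion criteria uses the phrase the same way: "planned surgical treatment during the trial (before a follow-up visit is completed".
- **PP definition.** Protocol 9.7 and SAP 3.3 require that patients "have completed the prescribed period of treatment and follow-up without significant deviations from the protocol".
- **Further treatment.** The synopsis, at the end of the Visit 3 (Day 5) description and directly after a sentence on Group B, says: "In case of worsening or preservation of the disease signs by the last therapy day, further treatment will be given in accordance with" the site's current standards of care.
- **Withdrawal.** Protocol 5.3.1 item 11 requires exclusion from the trial when "The patient receives or requires an additional therapy which might influence the trial results or patient's safety".
- **Timing and role.** Protocol 7.2 puts the primary assessment on the morning of Day 4, before that day's dose. ITT is the main analysis and PP is additional (protocol 9.1.2, SAP 3.3).

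**The concern.** The primary outcome is fixed on the morning of Day 4. A drug started later cannot change it, yet the exclusion as worded does not stop there. Patients whose disease persists have a reason to start a painkiller, an antibacterial or another throat product; recovered patients do not. PP membership can then depend on the outcome that PP is meant to analyse.

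PP is the only second population planned for the non-inferiority claim, so it will be read as support for the ITT result. Removing failures raises the response rate in whichever arm loses them. If both arms lose the same share, the difference shrinks towards zero. If the shares differ, the difference moves in favour of the arm that loses more.

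The documents also pull against each other: one passage foresees further treatment, while others prohibit most of the usual treatments and list their use as a serious deviation.

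**Working it through.** **The text.** The reach of the exclusion follows in four steps.

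1. SAP 3.2 excludes for use during the trial, and protocol 6.2.2 prohibits use for the whole trial period.
2. The synopsis, protocol 4.5 and the surgery criterion all place follow-up inside the trial.
3. The PP definition asks for follow-up, as well as treatment, without significant deviation.
4. No sentence ends the exclusion at the Visit 2 score.

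The literal combined reading therefore includes drugs started between the Day 4 score and the Day 6/7 call. It is an inference from several passages; no single sentence says it.

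**What would be recorded.** The visit schedule lists concomitant therapy at Visits 1, 2 and 3 and at unscheduled visits. Visit 4 is a telephone call for adverse events only. Capture after Day 4 therefore comes mainly from Visit 3 (Group B patients not recovered on Day 4), unscheduled visits, and drugs noted as action taken for an adverse event (protocol 8.3.4).

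**Size.** The plan gives no figure on this point, so the effect is shown over a range.

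Inputs:

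- Comparator rate 63% and margin 14.5 points (protocol 9.2). Truth at the margin puts Angal S at 63 − 14.5 = 48.5%.
- 140 per arm (protocol 9.2).
- Newcombe two-sided 90% interval (protocol 9.1.2, SAP 4.1.2), with the decision rule read as lower limit above −14.5 points.
- Assumption: f is the share of not-pain-free patients removed from PP. The documents do not give it.

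Formulas, per arm:

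- PP response rate = p / (p + (1 − p)(1 − f))
- Expected number removed = 140 × (1 − p) × f

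Example, f = 25% in both arms:

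- Angal S: 0.485 / (0.485 + 0.515 × 0.75) = 55.7%, with 140 × 0.515 × 0.25 = 18.0 removed.
- Comparator: 0.63 / (0.63 + 0.37 × 0.75) = 69.4%, with 140 × 0.37 × 0.25 = 12.9 removed.
- Difference: −13.8 points, against a true −14.5.

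The probability of declaring non-inferiority was simulated (200,000 trials or more per row):

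| f, Angal S | f, comparator | PP difference (points) | False non-inferiority in PP |
|---|---|---|---|
| 0 | 0 | −14.5 | 4.9% |
| 10% | 10% | −14.3 | 5.5% |
| 25% | 25% | −13.8 | 6.6% |
| 50% | 50% | −12.0 | 11.4% |
| 25% | 10% | −9.8 | 19.9% |
| 0 | 25% | −20.9 | 0.3% |

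The first row agrees with the one-sided 5% level in SAP 3.10, as it should. Equal and modest removal does little. Unequal removal does much more, in either direction.

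**The case against.** The case against is substantial, and most of it stands as a limit on the point.

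- **Exclusion is not automatic.** The drug must be in a prohibited class, and a sponsor representative evaluates each deviation. Protocol 11.3 describes a deviation as an intended departure from the protocol, and treatment that the protocol foresees is hard to call one. This stands. It does not remove the need for a rule, because the trial is open-label and no timing criterion guides the decision.
- **Item 11 of 5.3.1 may not apply.** Therapy begun after the Day 4 score cannot influence the primary result, although the item also covers patient safety and other results.
- **Capture is limited.** Visit 4 does not ask about concomitant drugs, so many late starts, especially in Group A, would go unseen.
- **Unrecovered is not the same as a primary failure.** Recovery is total TSS of 2 or less; the primary endpoint is a sore-throat item of zero. In the placebo-controlled lozenge trial used for the margin, 27 of 39 active-arm failures and 45 of 65 placebo failures on Day 4 were only mild, 69% in each. Large values of f are therefore hard to believe.
- **Direction by arm is unknown.** A reader might infer that the rule favours Angal S, because unrecovered Group A patients hand back the spray at Visit 2 while unrecovered Group B patients keep theirs until Visit 3. Removing 50% of failures in Group A and 25% in Group B would give a difference of −4.1 points and false non-inferiority of about 52%. The documents do not support choosing that sign. The further-treatment sentence sits in the Group B paragraph, and Group B has the extra visit at which drugs are recorded. If removal falls mainly on Group B, the PP analysis becomes harder to pass.

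**Conclusion.** The point holds as a gap in the PP rule. As worded, the exclusion for prohibited drugs runs past the Day 4 score, and the protocol foresees treatment in that window for patients still ill. PP membership can therefore depend on outcome.

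Its reach is limited to the additional PP analysis; the ITT error rate is unchanged. For equal removal of 10% to 25% of not-pain-free patients, false non-inferiority in PP goes from 4.9% to 5.5%–6.6%. Unequal removal gives anything from 0.3% to about 20% in the cases shown. All of this rests on truth at the margin, 140 per arm, the 90% Newcombe rule and an assumed f.

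Two stronger readings go too far. The documents do not say that every unrecovered patient given further treatment leaves PP, because sponsor review intervenes and recording is incomplete. Nor do they show that the rule favours the study drug, because neither f nor its direction is given. The change is worth making because it is cheap and removes a discretionary decision from an open-label trial.

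**What to change.** 1. In SAP 3.2, state that for Day 4 endpoints a prohibited drug leads to PP exclusion only if used between the start of the pre-trial window given in the entry criteria and the Visit 2 TSS assessment. For Day 5 endpoints in Group B, use the Visit 3 assessment as the cut-off.
2. Align the PP definition in protocol 9.7 and SAP 3.3, so that drugs started after the relevant assessment are not significant deviations for that endpoint.
3. Reconcile protocol 6.2.2 and item 11 of 5.3.1 with the synopsis sentence on further treatment, and say whether that sentence covers both arms. Which treatment is allowed, and when, is for the sponsor and investigators to settle.

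The cost is a few lines in the SAP and a short protocol clarification. The visits that set the cut-offs already record TSS and concomitant therapy, so no new visit or Visit 4 question is needed. For a drug started on Day 4 itself, the record should show whether it came before or after the score.

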3.3 Data sets for analysis

The intention-to-treat (ITT) population: All randomized subjects who have received at least one dose of the study drug/placebo and have completed at least one visit aimed at evaluation of the efficacy parameters (i.e., at least all the procedures of Visit 1).

According to the protocol (Section 9) and with reference to ICH E9 requirements, the ITT population will be considered to be a population for statistical analysis in the equivalence trials (including non-inferiority trials).

The per protocol (PP) population: All randomized subjects who have completed participation in the trial in accordance with the protocol (have completed the prescribed period of treatment and follow-up without significant deviations from the protocol).

A primary endpoint analysis will be conducted both for the ITT (main analysis) and PP populations (additional analysis).

Similarly, all efficacy endpoints will be analyzed both for the ITT and PP populations.

The safety population (safety): All randomized subjects who received at least one dose of the study drug/comparator drug and completed at least one

safety evaluation visit (i.e., at least Visit 1). As distinct from ITT population, the safety population will be analyzed depending on actually received treatment (not only prescribed) (in case of difference between the prescribed and received therapies).

The safety population will be used for all safety parameters including laboratory results, as well as for drug tolerability evaluation (see Section 2.3).

3.4 Subgroups

A subgroup analysis is not envisaged for this trial.

3.5 Data from various trial sites

This is a multicenter trial but data analysis for every particular trial site is not envisaged.

3.6 Missed data and outliers

At the database check, the expert in statistics authorized by the Sponsor and the data control and processing managers will analyze the trial results for questionable, missed and unanalyzable data, which will be the basis for the questions for investigators.

If possible, the investigators will eliminate the errors identified in CRFs and inform the Principal Investigator and authorized representatives of the Sponsor hereof. In case the identified data errors cannot be eliminated after the completion of the patients participation in the trial, the analysis of the resulting parameter sensitivity to questionable data will be conducted in the statistical analysis.

Information about the missed, questionable, and unanalyzable data will be summarized in the final clinical trial report.

The main analysis for the primary endpoint will be conducted without replacement for the missed, questionable, or unanalyzable data.

An additional analysis will be conducted with the data replacement (last observation carried forward); in this case, the last known TSS score will be carried to all subsequent control points.

All other data will be analyzed based on actually available information only, without data replacement.

Regarding abnormal test results, their clinical significance is evaluated by the Investigator during the trial with registration of AEs or adverse reactions, under control of the clinical trial specialists. Additional inquiries may be

forwarded to the trial sites (before the cut-off date) if clinical significance of the abnormal test results is hard to evaluate.

